mPATH-Lung (mobile Patient Technology for Health – Lung) is a digital outreach strategy for lung cancer screening (LCS). mPATH-Lung (a) queries the electronic health record (EHR) to identify potential screening candidates, (b) sends those individuals electronic invitations to visit a web-based LCS decision aid that confirms eligibility and provides personalized information, and (c) lets patients electronically request an LCS clinic appointment.

Our study design is depicted below in **Figure 1**. We will examine the effect of mPATH-Lung on receipt of Lung Cancer Screening (LCS) (**Aim 1**) in a patient-level pragmatic-design randomized controlled trial of 1320 primary care patients conducted in two large health networks with a catchment area extending to five states. We will send potentially eligible patients electronic invitations to visit our study website, which will determine eligibility and randomly assign patients to interact with either mPATH-Lung or an educational program about exercise for lung health. Patient knowledge, screening intent, and screening outcomes will be assessed by surveys and review of the Electronic Health Record EHR. Additionally, we will use mixed methods to elucidate the drivers of patients' LCS decisions (**Aim 2**), and assess implementation outcomes that will inform scalability and dissemination (**Aim 3**).

1.0 Introduction and Background

Lung cancer is the leading cause of cancer death in the United States.¹ In 2019, over 140,000 Americans will die of lung cancer, a number that is greater than those that will die from breast, prostate, and colorectal cancer combined.^{1,2} Over 80% of lung cancers are diagnosed at advanced stages when cure is not possible and 5-year survival is only 5-30%. However, if diagnosed early at a localized stage, 5-year survival is 56%.²

In 2011, the ground-breaking National Lung Screening Trial (NLST) demonstrated that annual screening with low-dose computed tomography (CT) decreases lung cancer mortality by 16-20%.^{3,4} Currently, several organizations (e.g., the US Preventive Services Task Force, the American Cancer Society, and the American Thoracic Society) endorse LCS for high-risk current and former smokers,⁵⁻⁷ and Medicare has approved LCS reimbursement for high-risk patients aged 55 to 77 years.⁸ Commercial insurers also cover LCS. Nonetheless, in 2015, fewer than 4% of eligible patients were screened.⁹

While LCS lowers lung cancer mortality, it also carries some risk. Thirty-nine percent of screened individuals in the NLST had at least one false positive after three screening rounds, leading to costly and sometimes invasive follow-up procedures that did not find cancer.^{3,10} Screening may also detect indolent cancer that never would have affected the patient during his or her lifetime – leading to overtreatment and possible physical, psychological, and financial harms.¹¹⁻¹³ Thus, current guidelines recommend and Medicare requires that providers engage in shared decision making with their patients before initiating screening.⁵⁻⁸

Helping patients make an informed LCS decision is a complex task because the harms and benefits vary according to individuals' risk factors. As an example, in the NLST, the number needed to screen to save one life ranged from 161 to 5276 depending on a patient's risk of developing lung cancer.¹⁴ Similarly, the number of false positives per life saved ranged from 65 to 1648.¹⁴ This wide variation highlights the critical importance of providing patients with personalized information so they can make an informed decision.

Shared decision making also requires helping patients consider their own unique values. Patients consider multiple factors when making decisions about cancer screening¹⁵⁻¹⁷ and weigh them differently (often unconsciously). Helping patients clarify which factors are most important to them, a process known as values clarification, is a critical aspect of a high-quality shared decision making process.¹⁸⁻²⁰ However, we have limited understanding of what factors drive patients' LCS decisions. Qualitative studies found that patients consider several factors in such decisions, including the mortality benefit, chance of false positives, emotional (anxiety) factors, and practical barriers (costs, transportation); but a weakness of current research is that how they weigh these factors to reach a decision is unclear.²¹⁻²⁷ Furthermore, to our knowledge, no studies have examined interventions to help patients clarify their values and preferences for LCS in routine care.

Multilevel barriers contribute to the low screening rates observed. Unfortunately, our current medical care system relies on time-pressured primary care providers to hold these complex discussions with patients, and primary care providers report lack of time as a leading barrier to providing guideline-recommended preventive care.²⁸⁻³⁴ In addition, many providers are unfamiliar with LCS guidelines.^{28,29,35-37} [name] (PI) and [name] (Co-I) were the first to document that only half of primary care providers could correctly identify 3 of 6 basic eligibility criteria for LCS.³⁸ Given these obstacles, providers rarely discuss or order LCS.^{34,36,39,40} Members of our team searched transcripts from over 5000 primary care visits and found that LCS was discussed with only 14 patients and explanation of potential harms of screening was virtually nonexistent.⁴¹ Similarly, many patients are unaware of the availability of LCS or its value.^{21,35}

Decision aids are a partial solution. Currently available decision aids can increase patients' knowledge of LCS,^{16,42-44} deliver some personalized information,^{16,45} and help patients make a screening decision.^{16,43} They can also mitigate providers' knowledge deficits by offering an

evidence-based, standardized format for providing patients with information about LCS. However, none provide patients with personalized information about the likelihood of the harms of screening, nor do they explicitly incorporate values into the decision making process.⁴⁵ Additionally, while physicians have endorsed LCS decision aids as helpful,²⁸ their use still requires time and they fail to address system barriers such as coordinating screening visits and insurance pre-approval. In two pilot studies conducted by members of our team, less than half of patients who wanted screening after watching an LCS decision aid received it.^{16,46}

To address these multilevel barriers to LCS and the need for personalized, shared decision making, our team has developed mPATH-Lung (mobile Patient Technology for Health – Lung), a user-friendly web-based application that can be systematically deployed to prepare patients and providers for meaningful shared decision making visits and help coordinate screening. mPATH-Lung addresses patient barriers by informing patients of LCS, providing them with personalized risk-benefit information, and helping them make decisions consistent with their values. mPATH-Lung addresses provider knowledge and time barriers by determining patient eligibility for LCS, assisting with routine counseling, and streamlining shared decision making visits. mPATH-Lung addresses system barriers by leveraging technology to reach patients where they are, facilitating LCS visit scheduling and insurance preapprovals, and automatically routing program usage information to primary care providers.

We designed mPATH-Lung with a screen adaptable design, allowing it to be used on smartphones or any other device. Over 75% of Americans own a smartphone.⁴⁷ While a digital divide exists for home broadband use, there is no racial/ethnic digital divide for smartphone ownership.⁴⁷ Smartphone ownership exceeds 67% even for those with annual household incomes less than \$30,000 or only a high school education,⁴⁷ and ownership continues to rise.

This study will examine mPATH-Lung's effectiveness, elucidate the factors that drive patients' screening decisions, and explore the potential for future dissemination and implementation using widely-accepted implementation frameworks.

2.0 Objectives

2.1 Primary Objective

- Determine the effectiveness of mPATH-Lung on receipt of LCS in a randomized pragmatic clinical trial of 1320 patients recruited from two large health networks, Wake Forest Baptist Health and the University of North Carolina at Chapel Hill.

2.2 Secondary Objectives

- Elucidate the drivers of patients' decisions to receive or forgo LCS through a values clarification exercise embedded within mPATH-Lung and supplemental semi-structured interviews of at least 50 patients.
- Assess several critical implementation outcomes (reach, acceptability, and appropriateness) to inform the sustainability and scalability of mPATH-Lung across diverse primary care settings

3.0 Study Population

3.1 Inclusion Criteria

Eligible patients will:

- Meet the Medicare criteria for LCS, as updated in February 2022:
 - Age 50 – 77 years
 - Smoked at least 20 pack years
 - Current smoker or quit smoking within the past 15 years
- Be scheduled to see a primary care provider within the health network in the next 3-4 weeks
- Have a patient portal account or cellphone number listed in the EHR

3.2 Exclusion Criteria

The following patients will be excluded:

- Patients flagged as needing a language interpreter in the EHR (electronic messages and intervention is delivered in English only)
- Those for whom LCS would be inappropriate:
 - Prior history of lung cancer
 - Chest CT within the last 12 months
 - Those with medical conditions predicting shorter life expectancy
- Patients whose home address is not within the state of North Carolina. (Due to telehealth guidelines)

3.3 Inclusion of Women and minorities

Women and men of all races and ethnicity who meet the above-described eligibility criteria are eligible for this trial.

4.0 Methods

4.1 Study Sites

The study will be conducted in two large academic-affiliated health networks (Wake Forest Baptist Health and UNC) that have over 200 community-based primary care clinics with approximately 900 PCPs and a catchment area covering all of North Carolina and extending to four neighboring states, including portions of rural Appalachia. In 2018 both networks saw 165,601 “ever smokers” who were potentially eligible for LCS based on age. Both health networks have the same EHR (EpicTM, Verona, WI) that is shared by all of their clinics.

LCS programs and usual care. Both networks have well-established LCS programs. Patients, who may self-refer to the LCS program, meet with a provider who confirms screening eligibility, conducts a shared decision making visit in accordance with CMS guidelines,⁸ and orders the screening CT. Afterwards, the LCS clinic communicates results to the patient and arranges any needed follow-up testing. Primary care providers may also order screening CTs directly, in which case they must conduct the shared decision making visit, communicate results, and order any needed follow-up testing. Both networks broadly advertise their LCS programs to patients via web campaigns, posters, and mailings. Despite these efforts, only 2% of those potentially eligible in 2018 (3,215 of 165,601) were screened.

4.2 Registration Procedures

Patients will be participating in a pragmatic trial in which patient data collection will occur by retrospective electronic chart review. All patients will receive current guideline-recommended care, and we will request a waiver of patient Informed Consent. Therefore, it is impractical to register patients with the Cancer Center, and any such registration would jeopardize patient confidentiality.

Following primary data collection, a subset of patients and clinic providers will participate in interviews and/or surveys related to the study's secondary objectives. No sensitive information will be collected from these participants. Therefore, we are requesting a waiver of signed consent. We will give these participants a study information sheet explaining the purpose of the study, the nature of the data to be collected, and the voluntary nature of their participation.

4.3 Participant Recruitment

We will identify eligible participants for this pragmatic trial in two phases.

Phase One (Sending electronic invitations): Each week we will query the EHR to identify potentially eligible participants based on the inclusion and exclusion criteria. We will oversample for non-white patients, and we will send identified patients an electronic invitation with an embedded hyperlink to our study website. The invitation text can be found in Appendix L. The hyperlink contains an anonymous study identifier unique to each patient, allowing us to track who visits the study website, an approach we successfully used in our pilot study.⁴⁶

As shown in Table 1, our preliminary data indicate the EHR accurately captures whether patients ever smoked (current or former smokers), but not years since quitting or pack-years. Therefore, our query will include all ever smokers, and the study webpage will gather additional detailed smoking history from patients to determine eligibility. Overall, 90% of our target sample has a patient portal account, mobile phone, or email address on file. Patients with an active portal account (defined as ≥ 1 logins over the past 90 days) will receive a message via MyChart. Those without a patient portal account will be sent a text message. Text message recipients will receive up to one additional reminder text message 3-7 days after the initial communication.

Table 1. Accuracy of Smoking History in the EHR Compared with Patient Self-Report

Self-reported smoking history	Accurately recorded
Ever smoker,	100% (336)
Years since quitting	44% (149)
Pack-years smoked (+/- 5	20% (35)

The study team will ensure each institution's patient consent forms cover the use of text messaging for this pragmatic trial before the invitations are sent.

[figure not shown]
Phase Two (Confirming eligibility via study website): When patients click on the hyperlink, it will take them to the study homepage. The site employs a user-friendly interface we have previously validated in low- and high-literacy patients.⁴⁹ The homepage will inform patients that the website was developed by researchers, will ask them a few questions to determine if they meet guideline criteria for lung cancer screening, and will then show them a brief video. The homepage will also specify that by proceeding, they understand their deidentified data may be used. This study qualifies for exemption under 45 CFR 46.101.

Potential participants will complete a brief self-survey on the website (Appendix A) to gather additional smoking history and determine if they meet eligibility criteria for LCS (as described above in Phase One). If patients are eligible for LCS, the study program will randomly assign them, stratified by health system network, to either mPATH-Lung or a control program about exercise for lung health using stored random

permuted blocks. Patients who are ineligible also will be shown the control program, but they will be excluded from the study.

4.4 mPATH-Lung Intervention

Planned Updates to mPATH-Lung: We have extensively tested the beta version of mPATH-Lung (Figure 2) which determines if patients are eligible for LCS via a self-survey, shows eligible patients a brief video decision aid, and then invites them to estimate their personal risks and benefits of screening by completing 8 survey items needed to calculate their predicted risk of developing lung cancer based on the validated Prostate, Lung, Colorectal and Ovarian Cancer Screening Trial Model 2012.^{14,46,50} Patients' risks of developing lung cancer are used to estimate their anticipated benefits (lives saved) and harms (false positives, invasive procedures, and complications) of screening, based on a model our team developed.^{45,46,51} This benefit-harm information is displayed to patients as an infographic, the format that maximizes engagement and comprehension, particularly for patients with low literacy or numeracy skills.^{52,53} Patients who decline to estimate their personal risks are shown an infographic summarizing the benefits and harms for the average risk individual in the NLST cohort. The beta version concludes by asking patients if they want to receive screening and then providing them with the phone number for the LCS clinic.

In preparation for this proposed trial, we will update the beta version with four new features outlined below.

Video Decision Aid (Appendix B): The beta version of mPATH-Lung includes a short animated proof of concept video that reviews the general risks and benefits of LCS. We will replace this with an extensively tested, professionally developed LCS video decision aid that includes a strong message about the importance of tobacco cessation.^{42,44,54} The video will explicitly address the risks and benefits outlined in Table 2, including screening-related anxiety and overscreening.

Values Clarification Exercise (Appendix C): Helping patients clarify how they balance the potential benefits and harms of screening is a critical element of shared decision making. An explicit values clarification exercise can help patients make a screening decision consistent with their values.¹⁸ Patients will complete the exercise immediately after seeing their personalized risk-benefit infographic (see Figure 2, fourth panel from left). The exercise will be adapted from previously tested values clarification instruments, including some developed by our team members.^{15,55} First,

patients will complete a rating exercise, in which they will rate the importance of the risks and benefits, or “attributes,” of the screening decision (e.g., 193 out of 1000 chance of a false positive, or 10 lives saved out of 1000) individually on a 5-point Likert scale. Attributes rated will be the same as the risks and benefits of screening covered in the video decision aid (Table 2). Afterwards, patients will complete a ranking exercise, in which they will indicate their top two attributes in order of personal importance. Finally, patients will indicate their screening preference. To maximize readability, clarity, and comprehension, we will cognitively test the values clarification exercise using “think aloud” exercises with 10-15 patients who are eligible for LCS. In this pre-test, patients will complete the values clarification exercise and a cognitive interview to help us evaluate each item’s performance (e.g., whether the content is understood in the intended manner, ease of completion) and clarity of the instructions. We will use results to iteratively improve materials between pre-testing sessions (e.g., revise wording for clarity). Patients who participate in this pre-testing phase will receive \$50 for their time and will be ineligible for the larger study.

Electronic Summaries: On completion of mPATH-Lung, participants will be given the option to download a program summary including their personalized risk-benefit infographic, values clarification results, and screening decision.

Electronic Requests for an LCS Clinic Visit: We will update mPATH-Lung so that patients can request an LCS clinic appointment directly from the program, mitigating the scheduling barrier. mPATH-Lung will present a webform to patients who indicate a desire to be screened. A study team member will send this information to the lung cancer screening clinic staff via the EHR so that they may contact the patient to schedule the appointment. The information in the webform will be accompanied by a statement that the patient used mPATH-Lung, was confirmed eligible for LCS, and is requesting a screening clinic appointment. Patients’ answers to each eligibility item will be included to aid in insurance precertification so that the shared decision making visit can end with same-day screening if indicated. For patients who request a screening clinic appointment, the study team member will also upload a copy of the patient’s program summary to the EHR. While patients will still engage in the Medicare-mandated shared decision making visit in the LCS clinic or primary care office, the easily retrieved mPATH-generated program summary in the EHR will allow the visit to proceed efficiently.

Patients who indicate an uncertainty about screening will be encouraged to discuss their concerns with their primary care provider at their upcoming appointment. As noted in our study inclusion criteria, all invited patients will have a primary care appointment in the next 3-4 weeks.

White Box Testing: We will use white box testing methods⁵⁶ to ensure the revised version of mPATH-Lung functions as planned. White box testing involves entering sequences of data purposefully designed to test all failsafes and features of the program, including the accuracy of data collection.

Usability Testing (Appendix M): Prior to commencing the pragmatic trial, we will conduct usability testing to ensure the mPATH-Lung program is appropriately designed for the target population. A study team member will meet individually with participants to observe them using the mPATH-Lung program following a Concurrent Think Aloud method.

Table 2. Risks/benefits (attributes) of screening addressed in mPATH-Lung

Averting death from lung cancer
Worry/anxiety over an abnormal scan
Experiencing a false alarm
Undergoing an invasive procedure
Having a serious complication from an unnecessary procedure
Finding a slow growing or harmless cancer and needlessly treating it
Radiation exposure

Final mPATH-Lung Structure: Patients will proceed through mPATH-Lung as outlined below.

1. Study website determines LCS eligibility
2. If eligible, LCS decision aid video displayed
3. Personalized risks-benefits of screening calculated and displayed as an infographic.
4. Valued clarification exercise conducted
5. Patient asked if they would like to receive LCS
 - a. If patient answers “yes” or “maybe”: webform presented for patient to request a LCS visit of desired
 - b. If patient answers “no”: patient encouraged to discuss LCS with primary care provider
6. Patient given option to download an electronic summary

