5.2 Secondary Outcomes

- 5.2.1 LCS screening decisions: LCS screening decisions will be captured by the mPATH-Lung program in the mPATH-Lung group only. (Time frame = post-intervention)
- 5.2.2 LCS clinic visits scheduled: The proportion of patients in each arm who have scheduled a LCS clinic visit will be captured by querying the EHR at each site.
- 5.2.3 LCS clinic visits completed: The proportion of patients in each arm who have completed a LCS clinic visit will be captured by querying the EHR at each site.
- 5.2.4 LCS scans ordered: The proportion of patients in each arm for whom a LCS scan was ordered will be captured by querying the EHR at each site.
- 5.2.5 LCS Clinic referral requested through mPATH
- 5.2.6 Lung RADS Results: The results of all chest CTs will be captured by querying the EHR at each site.
- 5.2.7 LCS false positives: A false positive scan will be defined as a Lung-RADS 3 or 4 result with a negative completed work-up for lung cancer or no diagnosis of lung cancer within 12 months of the scan.
- 5.2.8 Invasive procedures following LCS scan: We will query the EHR at each site to determine the number and proportion of patients in each arm who undergo an invasive procedure to investigate an abnormal LCS scan.
- 5.2.9 Complications following LCS: We will query the EHR at each site and conduct a blinded chart review to determine the number and proportion of patients in each arm who experience a complication from an invasive procedure done to investigate an abnormal LCS scan.
- 5.2.10 Number of diagnosed lung cancers (detected by screening or other) within 16 months of randomization
- 5.2.11 Whether diagnosed lung cancers were detected incidentally or related to screening
- 5.2.12 Stage of lung cancers diagnosed
- 5.2.13 Overscreening: We will determine the proportion of patients with screen diagnosed lung cancer in the mPATH-Lung and control groups who are deemed too ill for potentially curative surgery by blinded chart review.
- 5.2.14 Reach of digital outreach strategy: Reach of the digital outreach strategy is defined as the proportion of patients who complete the website study eligibility questions. The denominator includes all patients who were sent an invitation, regardless of full program completion and whether or not they were subsequently determined to be eligible for LCS.

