6.4 Sample Size and Power

In 2015 (the year Medicare approved payment for LCS), only 3.9% of eligible Americans were screened.⁹ Given that national screening rates are expected to increase, we will conservatively assume the screening rate in the control group will be 10%. A total sample size of 1320 patients (approximately 660 in each group) will provide 90% power for detecting a 6% absolute difference in screening rates at the 5% two-sided level of significance and approximately 80% power for detecting a 5% absolute difference in screening. Because our primary outcome measure is determined by electronic health record review and not surveys, there will be no loss to follow-up.

We anticipate sending approximately 26,000 electronic invitations to identify and accrue 1320 eligible patients. This sample size of 26,000 invitations will allow us to estimate the *Reach* of the electronic invitations to within $\pm 0.6\%$. Our sample size of 660 patients in the mPATH-Lung arm will allow us to estimate the *Reach* of mPATH-Lung (the proportion of those who complete it) to within $\pm 3.8\%$. Our sample size of 660 patients in the mPATH-Lung arm will allow us to estimate the mean *Acceptability* score to within ± 0.076 SD. Due to the highly pragmatic nature of this study, our planned sample size will stay 660, but we may over-enroll because it takes time to change the mPATH codebase once accrual targets are reached. While we are changing the codebase, participants who received invitations may continue to visit the mPATH web app and be randomized. Therefore, we acknowledge we may over-enroll by a few participants.

Following completion of primary data collection, we will invite all primary care providers who had at least one patient randomized to mPATH-Lung to respond to a brief emailed survey. We expect 466 primary care providers will have at least 1 patient in the mPATH-Lung arm (based on the binomial probability assuming 660 patients in the mPATH-Lung arm and an equal probability of seeing one of 890 health system providers). Based on our prior studies surveying providers (with response rates of 40% - 60%),^{38,70} we conservatively estimate 30% will respond which will yield approximately 140 completed surveys. Our sample size of 140 providers will allow us to estimate the mean *Appropriateness* score to within ± 0.17 SD.

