6.5 Accrual Rate

In our prior pilot study limited to patients with active portal accounts in a single health system, it required 10 weeks to identify 1000 potentially eligible patients, of whom 35% (349) completed our study program, and 10% (99) were found to be eligible for LCS, yielding 10 patients per week.¹ For this pragmatic trial, we will accrue patients from two health networks and also include patients with cellphone numbers or email addresses, significantly expanding the pool of eligible participants. Patients without portal accounts may be less likely to respond, so we conservatively estimate that we will accrue patients at half the rate (5%) of our pilot study. Therefore, we will send invitations to 260 patients per week (130 at Wake Forest and 130 at UNC) to accrue 13 patients per week, completing accrual over 2 years. We will oversample for non-white patients. We will monitor accrual rates and increase the number of invitations sent as needed.

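### Overall Reach is an unweighted proportion of invitees although non-white patients are oversampled, so the figure describes the oversampled mix and not the EHR-identified pool

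*Combined protocol and SAP*

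**What the plan says.** - **Selection of invitees.** Section 4.3, Phase One: "We will oversample for non-white patients, and we will send identified patients an electronic invitation". Section 6.5 repeats it: "We will oversample for non-white patients. We will monitor accrual rates and increase the number of invitations sent as needed". No sampling fraction or target share is given in either place.
- **Split by network.** Section 6.5 fixes the weekly invitations at "130 at Wake Forest and 130 at UNC".
- **Definition of Reach.** Section 5.2.14: "Reach of the digital outreach strategy is defined as the proportion of patients who complete the website study eligibility questions". It adds: "The denominator includes all patients who were sent an invitation, regardless of full program completion".
- **Precision.** Section 6.4: "This sample size of 26,000 invitations will allow us to estimate" Reach of the invitations to within ±0.6%.
- **Analysis.** Section 6.2 plans descriptive Reach by patient sociodemographics and invitation modality, and a logistic regression of Reach on patient characteristics. Sampling weights, standardisation to the source pool and a design-based variance are not mentioned.
- **Purpose.** Section 2.2 lists reach among the implementation outcomes meant to inform sustainability and scalability.

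**The concern.** Oversampling a group is sound design when that group's results are wanted with good precision. It also means that the pooled, unweighted proportion no longer estimates the response in the population from which the sample came. Two studies with identical Reach in every race group would report different overall Reach simply because they oversampled to different degrees. Here the degree is unstated, and invitation numbers may be raised during accrual, so the invited mix could also drift.

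Reach is intended to tell a health system what share of its query-identified patients would respond. A crude figure with a very narrow interval could be taken as the answer to that question when it answers a different one. With about 26,000 invitations, sampling error is small enough for dependence on the mix to be the larger uncertainty.

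**Working it through.** **1. The plan's own figure.** With n = 26,000 (section 6.4) and the worst case p = 0.5, the simple-random-sample half-width is 1.96 × √(0.25/26,000) = 0.608%. This reproduces ±0.6%. At 35%, the programme completion rate in the pilot (section 6.5), it is 1.96 × √(0.35 × 0.65/26,000) = 0.580%. The stated precision is right for the crude proportion and contains no allowance for weighting.

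**2. Shift of the crude figure.** Let W be the non-white share of the EHR-identified pool, f the non-white share of invitees, and d the difference in Reach between white and non-white patients. Then

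pool Reach minus crude Reach = (f − W) × d.

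The documents give none of W, f or d. All values below are assumptions.

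| W | f | Reach, white / non-white | Crude | Standardised | Shift (points) |
|---|---|---|---|---|---|
| 25% | 50% | 35% / 25% | 0.5×35 + 0.5×25 = 30.0% | 0.75×35 + 0.25×25 = 32.5% | 2.5 |
| 25% | 50% | 10% / 6% | 8.0% | 9.0% | 1.0 |
| 25% | 40% | 15% / 10% | 0.6×15 + 0.4×10 = 13.0% | 13.75% | 0.75 |
| any | any | no difference | same | same | 0 |

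**3. Precision of a standardised estimate.** With equal variance in both strata, the design effect is W²/f + (1 − W)²/(1 − f).

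- W = 25%, f = 40%: 0.0625/0.40 + 0.5625/0.60 = 1.09. Half-width at p = 0.5: 0.608 × √1.09 = ±0.64%.
- W = 25%, f = 50%: 0.0625/0.50 + 0.5625/0.50 = 1.25. Half-width at p = 0.5: 0.608 × √1.25 = ±0.68%.

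Using the assumed response rates themselves, the half-width is 1.96 × √(Σ W_h² p_h(1 − p_h)/n_h), where W_h is the pool share, p_h the Reach and n_h the number invited in stratum h. For the first three rows of the table this gives ±0.64%, ±0.40% and ±0.44%. The loss of precision is small.

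**4. Network.** Section 4.1 gives 165,601 age-eligible ever smokers for both networks together and no split. If the networks are of equal size, 130:130 is proportional and nothing shifts. If the true split were 60:40 (assumed), the design effect would be 0.36/0.5 + 0.16/0.5 = 1.04, and a 5-point gap between networks would shift the crude figure by 0.10 × 5 = 0.5 point. Which case applies cannot be told from the documents.

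**The case against.** The strongest reply is that Reach is explicitly defined over invitees, so the crude proportion and its interval estimate exactly what was defined. The plan also reports Reach by sociodemographic group. Race-specific Reach does not depend on the oversampling fraction, and an adopting system can apply its own mix to it. Standardising to the two study networks only replaces one local mix with another. This stands to a large extent. It means the crude figure is a different estimand and not a miscalculation, and that the stratum-specific results should stay. It does not supply an overall figure for the pool that was queried, because the regression gives associations, and no section says that the source counts needed for standardisation will be kept. The query runs weekly on patients with an upcoming visit, so the pool may be hard to rebuild later.

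Three stronger readings are tempting but not supported:

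- **That invitation probabilities are unequal by network.** The network sizes are not given, so the equal split may be proportional.
- **That ±0.6% is wrong, or should read ±0.7%.** It is correct for the crude proportion. Under the assumed response rates above, the standardised half-widths are ±0.64% or less.
- **That a known error of 2.5 points exists.** That is the largest of the three illustrations, every input is assumed, and the shift is zero if Reach does not differ by race.

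**Conclusion.** The concern holds as a gap in the reporting of one secondary outcome. Non-white patients are oversampled at an unstated rate, overall Reach is unweighted, and nothing planned converts it to the EHR-identified pool. The shift is (f − W) × d: 0.75 to 2.5 points for a 25% source share, 40% to 50% of invitees and gaps of 5 to 10 points, and zero without a gap. These ranges rest entirely on assumed values. The effect on precision is minor. The network split is an open question. Randomisation, the primary comparison and its type I error are not touched, because oversampling acts before randomisation.

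**What to change.** 1. In 4.3 and 6.5, state the oversampling fraction or target share, and log any change to it during accrual.
2. Keep de-duplicated counts of unique query-eligible patients and unique invited patients by race stratum and by network. Weekly totals alone are not enough: a patient not invited one week may reappear in a later query, so weekly ratios do not give a patient's chance of invitation.
3. In 5.2.14 and 6.2, report overall Reach standardised to the race (and network) mix of the EHR-identified pool, with a design-based confidence interval, beside crude Reach and the planned stratum-specific Reach. Add network to the breakdown.
4. In 6.4, say that ±0.6% applies to the crude proportion of invitees and that the standardised estimate will be slightly less precise: about ±0.64% to ±0.68% at p = 0.5 under assumed design effects of 1.09 to 1.25, and less at lower Reach.

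The cost is some added data retention, a few lines of text and slightly wider intervals. Recruitment, randomisation and sample size do not change.
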